### 9.6.3 Demographic and Baseline Characteristics

The relevant demographic and baseline characteristics will be assessed using summary tables. No statistical hypothesis tests will be performed on these characteristics. The number and percentage of participants screened and randomized and the primary reasons for screening failure and discontinuation will be displayed. Demographic variables, baseline characteristics, prior and concomitant vaccinations and therapies will be summarized either by descriptive statistics or categorical tables.

### 9.7 Interim Analyses

There are no planned interim analyses for this study.

### 9.8 Multiplicity

No adjustment will be made for multiplicity.

## 9.9 Sample Size and Power Calculations

### 9.9.1 Sample Size and Power for Immunogenicity Analyses

This is a descriptive study. This study will randomize approximately 45 participants to receive V114. It is assumed that approximately 38 participants will be evaluable for PP immunogenicity analyses at 30 days PD3 (based on an 85% evaluability rate), and 36 participants will be evaluable for PP immunogenicity analyses at 30 days PD4 (based on an 80% evaluability rate).

The width of the 95% CIs for the serotype-specific IgG GMCs depends on the sample size, variability of the natural log concentrations, and the magnitude of the IgG GMC. In [Table 5](#), the 95% CIs for various hypothetical IgG GMCs at 30 days PD3 and various hypothetical standard deviation estimates for the natural log titers are displayed.

Table 5 95% CIs for Varying Hypothetical IgG GMCs and Varying Standard Deviations

Standard Deviation of Natural Log Titers †	Serotype-specific IgG GMC †		
	1	5	10
1.0	(0.73, 1.37)	(3.64, 6.87)	(7.28, 13.74)
1.5	(0.62, 1.61)	(3.10, 8.06)	(6.21, 16.11)
2.0	(0.53, 1.89)	(2.65, 9.44)	(5.29, 18.89)

Based on 38 evaluable participants.

† The estimates of the standard deviation and IgG GMCs are representative of those observed in a previous MSD study.

CI = confidence interval; GMC = geometric mean concentration; IgG = immunoglobulin G.

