Sample Size and Power	Immunogenicity: This study will allocate approximately 45 participants to V114. It is assumed that approximately 38 participants will be evaluable for immunogenicity analyses at 30 days PD3 (85% evaluability rate), and approximately 36 participants will be evaluable for immunogenicity analyses at 30 days PD4 (80% evaluability rate). There are no hypotheses to be evaluated, but Section 9.9.1 provides information about the expected variability of the IgG GMCs given the sample size.

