### 9.6.1 Statistical Methods for Immunogenicity Analyses

This section describes the statistical methods that address the primary and secondary immunogenicity objectives.

Immunogenicity analyses will be conducted for each of the 15 pneumococcal serotypes in V114 separately. To address the primary immunogenicity objectives, evaluation of the IgG response rates and GMCs at 30 days after the third dose of V114 will include descriptive summaries and 95% CIs. For IgG response rates, the CIs will be calculated based on the exact binomial method proposed by Clopper and Pearson [CLOPPER, C. J. and PEARSON, E. S. 1934]. For IgG GMCs, point estimates will be calculated by exponentiating the estimates of the mean of the natural log values. The CIs will be derived by exponentiating the CIs of the mean of the natural log values based on the t-distribution.

To address the secondary immunogenicity objective, evaluation of the IgG GMCs at 30 days after the fourth dose of V114 will include descriptive summaries and 95% CIs.

The primary and secondary endpoints may be summarized separately as soon as complete data for the specified time points become available.

A detailed analysis strategy for immunogenicity endpoints is listed in [Table 3](#).

Table 3 Analysis Strategy for Key Immunogenicity Variables

Endpoint/Variable (Description, Time Point)	Primary vs. Supportive Approach †	Statistical Method	Analysis Population	Missing Data Approach
Primary Endpoints				
IgG response rates at 30 days PD3	P	Descriptive Statistics (estimate, 95% CI)	PP	Missing data will not be imputed
	S		FAS	
IgG GMCs at 30 days PD3	P	Descriptive Statistics (estimate, 95% CI)	PP	Missing data will not be imputed
	S		FAS	
Secondary Endpoint				
IgG GMCs at 30 days PD4	P	Descriptive Statistics (estimate, 95% CI)	PP	Missing data will not be imputed

† P=Primary approach; S=Supportive approach.  
CI = confidence interval; FAS = Full Analysis Set; GMC = geometric mean concentration;  
IgG = immunoglobulin G; PP = Per-Protocol.

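### Table 5's nine GMC confidence intervals use the normal quantile 1.96, but Section 9.6.1 commits to t-based intervals, which are about 3.4% wider on the log scale

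*Combined protocol and SAP*

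**What the plan says.** Section 9.6.1 of the combined protocol and SAP fixes the interval method for GMCs: "The CIs will be derived by exponentiating the CIs of the mean of the natural log values based on the t-distribution".

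Section 9.9.1 expects that "approximately 38 participants will be evaluable for PP immunogenicity analyses at 30 days PD3 (based on an 85% evaluability rate"). It introduces Table 5 as showing "the 95% CIs for various hypothetical IgG GMCs at 30 days PD3 and various hypothetical standard deviation estimates". The table gives nine 95% confidence intervals, crossing GMCs of 1, 5 and 10 with SDs of the natural log values of 1.0, 1.5 and 2.0. Its footnote reads "Based on 38 evaluable participants". Neither the text nor the footnotes name the quantile used or mention a normal approximation.

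The summary in Section 9.1 directs the reader to this material: "Section 9.9.1 provides information about the expected variability of the IgG GMCs given the sample size".

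**The concern.** The method in Section 9.6.1, applied to the inputs of Table 5, does not return the intervals in Table 5. The printed intervals are narrower in all nine cells, as they would be if a normal quantile had replaced the t quantile.

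Section 9.3 states that this is an estimation study without formal hypothesis tests, so expected interval width does the job that power does elsewhere. Table 5 is the only place where the plan states a precision for immunogenicity. If it is too narrow, the plan describes its precision slightly too favourably, and a reader who follows the SAP's own method cannot reproduce it.

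**Working it through.** **Inputs.** All are from Section 9.9.1 except the method, which is from Section 9.6.1.

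- Evaluable n = 38 (45 × 0.85 = 38.25), so df = 37
- SD of natural log values: 1.0, 1.5, 2.0
- GMC: 1, 5, 10
- Two-sided 95% confidence
- Method: t interval for the mean natural log value, exponentiated

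**Formula.** Limits = GMC × exp(± q × SD / √n), where q is the quantile and √38 = 6.1644.

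**Step 1: reproduce the printed table.** With q = 1.9600, the log half-width is 1.9600 / 6.1644 × SD = 0.3179 × SD. For SD 1.0 and GMC 5:

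- lower: 5 × exp(−0.3179) = 3.638, printed 3.64
- upper: 5 × exp(+0.3179) = 6.872, printed 6.87

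All 18 limits match to two decimals in this way.

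**Step 2: apply the planned method.** With q = t(0.975, 37) = 2.0262, the log half-width is 2.0262 / 6.1644 × SD = 0.3287 × SD. For the same cell:

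- lower: 5 × exp(−0.3287) = 3.599
- upper: 5 × exp(+0.3287) = 6.946

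None of the 18 printed limits matches.

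| SD | GMC | Printed | t, 37 df |
|---|---|---|---|
| 1.0 | 1 | (0.73, 1.37) | (0.72, 1.39) |
| 1.0 | 5 | (3.64, 6.87) | (3.60, 6.95) |
| 1.0 | 10 | (7.28, 13.74) | (7.20, 13.89) |
| 1.5 | 1 | (0.62, 1.61) | (0.61, 1.64) |
| 1.5 | 5 | (3.10, 8.06) | (3.05, 8.19) |
| 1.5 | 10 | (6.21, 16.11) | (6.11, 16.37) |
| 2.0 | 1 | (0.53, 1.89) | (0.52, 1.93) |
| 2.0 | 5 | (2.65, 9.44) | (2.59, 9.65) |
| 2.0 | 10 | (5.29, 18.89) | (5.18, 19.30) |

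**Step 3: rule out rounding.** Solving the printed limits for q at n = 38, with rounding allowed for, confines q to 1.9597 to 1.9604. That excludes 2.026.

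**Step 4: rule out a different n.** Under the t method the number of matching limits out of 18 is:

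- n = 36 to 39: 0
- n = 40: 3
- n = 41: 5
- n = 42: 2
- n = 43 to 45: 0

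Under the normal quantile, checked for n = 36 to 41, only n = 38 gives 18 of 18. The next best is n = 39 with 4.

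**Step 5: size.**

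- Log-scale width, planned over printed: 2.0262 / 1.9600 = 1.0338, that is 3.4% wider at every SD.
- Concentration-scale width, planned over printed: 1.0350 (SD 1.0), 1.0364 (SD 1.5), 1.0385 (SD 2.0).

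**Step 6: compare with sampling variation in the SD.** With 37 df, the 95% range of the sample SD relative to the true SD is 0.773 to 1.227. If the true SD equals the tabled one, a t interval is at least as narrow as printed when the chi-square variable on 37 df is at most 37 × (1.9600 / 2.0262)² = 34.62. That has probability 0.419.

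**The case against.** The strongest reply is that Section 9.6.1 governs the analysis of observed data, whereas Table 5 is a planning display for hypothetical values. Treating a tabled SD as fixed and using a normal quantile is a common planning approximation, and under it the table is computed correctly. Nothing depends on the result either: there is no width target or success criterion for the GMCs, and the Document History attributes the cut from about 100 to about 45 participants to enrolment difficulties. The gap is also small beside the coarseness of the table, where the log-scale width rises by 50% and then 33% from one SD row to the next. A t interval with 40 evaluable participants has a half-width of 2.0227 / √40 = 0.320 × SD, close to the printed 0.318 × SD.

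Most of this stands as a limit on importance. It does not remove the mismatch, because the approximation is undeclared. Section 9.9.1 presents the figures as 95% intervals at "various hypothetical standard deviation estimates for the natural log titers are displayed". For an estimated SD of 1.0 and an estimated GMC of 5, the interval the plan would report is (3.60, 6.95). The t calculation needs no further input, so the approximation gains nothing.

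**Conclusion.** The point holds. Table 5 rests on the normal quantile, while the plan commits to the t-distribution. At each tabled SD the planned interval is 3.4% wider on the log scale, and 3.5% to 3.8% wider on the concentration scale. All nine cells err in the favourable direction.

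The consequence is minor. Variation in the estimated SD will move the actual widths far more, and about 42% of the time a t interval would be no wider than printed. Sample size, final analysis and conclusions are unaffected. The sizes assume 38 evaluable participants and take the tabled SD as the estimate that enters the interval. The correction is optional but worth making. The defect is best described as an undeclared approximation that disagrees with the analysis method, not as a slip in calculation.

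**What to change.** Replace the limits in Table 5 with the t-based values in the last column of the comparison above, and add to the footnote that they use the t-distribution with 37 degrees of freedom, as in Section 9.6.1.

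A lesser remedy is to keep the printed limits and add a footnote that they are a normal approximation while the final intervals use the t-distribution. That removes the inconsistency but leaves the stated precision slightly too favourable.

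The cost is one table and its footnote. Enrolment and analysis do not change. The stated precision becomes slightly less favourable.

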### 9.9.2 Sample Size and Power for Safety Analyses

The probability of observing at least 1 SAE in this study depends on the number of participants vaccinated and the underlying incidence of participants with an SAE in the study population. Calculations below assume that 100% of the randomized participants will be evaluable for safety analyses. There is an 80% chance of observing at least 1 SAE among 45 participants if the underlying incidence of an SAE is 3.5% (1 of every 28 participants receiving the vaccine). There is a 50% chance of observing at least 1 SAE among 45 participants if the underlying incidence of an SAE is 1.5% (1 of every 65 participants receiving the vaccine). If no SAEs are observed among 45 participants, this study will provide 97.5% confidence that the underlying percentage of participants with an SAE is <7.9% (1 in every 13 participants).

## **9.10 Subgroup Analyses**

Subgroup analyses (eg, sex = female vs male) will be performed for the primary immunogenicity endpoints and selected safety endpoints (summary of AEs). Details of subgroup analyses will be documented in the sSAP.

## **9.11 Compliance (Medication Adherence)**

The number and proportion of randomized participants receiving V114 will be summarized.

## **9.12 Extent of Exposure**

The extent of exposure will be summarized by the number and proportion of randomized participants administered V114.

## 10 SUPPORTING DOCUMENTATION AND OPERATIONAL CONSIDERATIONS

### 10.1 Appendix 1: Regulatory, Ethical, and Study Oversight Considerations

#### 10.1.1 Code of Conduct for Clinical Trials

Merck Sharp & Dohme LLC, Rahway, NJ, USA (MSD)

#### Code of Conduct for Interventional Clinical Trials

##### I. Introduction

###### A. Purpose

MSD, through its subsidiaries, conducts clinical trials worldwide to evaluate the safety and effectiveness of our products. As such, we are committed to designing, implementing, conducting, analyzing, and reporting these trials in compliance with the highest ethical and scientific standards. Protection of participants in clinical trials is the overriding concern in the design and conduct of clinical trials. In all cases, MSD clinical trials will be conducted in compliance with local and/or national regulations (including all applicable data protection laws and regulations), and International Council for Harmonisation Good Clinical Practice (ICH-GCP), and also in accordance with the ethical principles that have their origin in the Declaration of Helsinki.

###### B. Scope

Highest ethical and scientific standards shall be endorsed for all clinical interventional investigations sponsored by MSD irrespective of the party (parties) employed for their execution (e.g., contract research organizations, collaborative research efforts). This Code is not intended to apply to trials that are observational in nature, or which are retrospective. Further, this Code does not apply to investigator-initiated trials, which are not under the full control of MSD.

##### II. Scientific Issues

###### A. Trial Conduct

###### 1. Trial Design

Except for pilot or estimation trials, clinical trial protocols will be hypothesis-driven to assess safety, efficacy and/or pharmacokinetic or pharmacodynamic indices of MSD or comparator products. Alternatively, MSD may conduct outcomes research trials, trials to assess or validate various endpoint measures, or trials to determine patient preferences, etc.

The design (i.e., participant population, duration, statistical power) must be adequate to address the specific purpose of the trial and shall respect the data protection rights of all participants, trial site staff and, where applicable, third parties. Participants must meet protocol entry criteria to be enrolled in the trial.

###### 2. Site Selection

MSD selects investigative sites based on medical expertise, access to appropriate participants, adequacy of facilities and staff, previous performance in clinical trials, as well as budgetary considerations. Prior to trial initiation, sites are evaluated by MSD personnel (or individuals acting on behalf of MSD) to assess the ability to successfully conduct the trial.

###### 3. Site Monitoring/Scientific Integrity

Investigative trial sites are monitored to assess compliance with the trial protocol and Good Clinical Practice (GCP). MSD reviews clinical data for accuracy, completeness, and consistency. Data are verified versus

source documentation according to standard operating procedures. Per MSD policies and procedures, if potential fraud, scientific/research misconduct, privacy incidents/breaches or Clinical Trial-related Significant Quality Issues are reported, such matters are investigated. When necessary, appropriate corrective and/or preventative actions are defined and regulatory authorities and/or ethics review committees are notified.

#### **B. Publication and Authorship**

Regardless of trial outcome, MSD commits to publish the primary and secondary results of its registered trials of marketed products in which treatment is assigned, according to the pre-specified plans for data analysis. To the extent scientifically appropriate, MSD seeks to publish the results of other analyses it conducts that are important to patients, physicians, and payers. Some early phase or pilot trials are intended to be hypothesis-generating rather than hypothesis testing; in such cases, publication of results may not be appropriate since the trial may be underpowered and the analyses complicated by statistical issues such as multiplicity.

MSD's policy on authorship is consistent with the recommendations published by the International Committee of Medical Journal Editors (ICMJE). In summary, authorship should reflect significant contribution to the design and conduct of the trial, performance or interpretation of the analysis, and/or writing of the manuscript. All named authors must be able to defend the trial results and conclusions. MSD funding of a trial will be acknowledged in publications.

### **III. Participant Protection**

#### **A. Regulatory Authority and Ethics Committee Review (Institutional Review Board [IRB]/Independent Ethics Committee [IEC])**

All protocols and protocol amendments will be submitted by MSD for regulatory authority acceptance/authorization prior to implementation of the trial or amendment, in compliance with local and/or national regulations.

The protocol, protocol amendment(s), informed consent form, investigator's brochure, and other relevant trial documents must be reviewed and approved by an IRB/IEC before being implemented at each site, in compliance with local and/or national regulations. Changes to the protocol that are required urgently to eliminate an immediate hazard and to protect participant safety may be enacted in anticipation of ethics committee approval. MSD will inform regulatory authorities of such new measures to protect participant safety, in compliance with local and/or national regulations.

#### **B. Safety**

The guiding principle in decision-making in clinical trials is that participant welfare is of primary importance. Potential participants will be informed of the risks and benefits of, as well as alternatives to, trial participation. At a minimum, trial designs will take into account the local standard of care.

All participation in MSD clinical trials is voluntary. Participants enter the trial only after informed consent is obtained. Participants may withdraw from an MSD trial at any time, without any influence on their access to, or receipt of, medical care that may otherwise be available to them.

#### **C. Confidentiality**

MSD is committed to safeguarding participant confidentiality, to the greatest extent possible, as well as all applicable data protection rights. Unless required by law, only the investigator, Sponsor (or individuals acting on behalf of MSD), ethics committee, and/or regulatory authorities will have access to confidential medical records that might identify the participant by name.

#### **D. Genomic Research**

Genomic research will only be conducted in accordance with a protocol and informed consent authorized by an ethics committee.

#### **IV. Financial Considerations**

##### **A. Payments to Investigators**

Clinical trials are time- and labor-intensive. It is MSD's policy to compensate investigators (or the sponsoring institution) in a fair manner for the work performed in support of MSD trials. MSD does not pay incentives to enroll participants in its trials. However, when enrollment is particularly challenging, additional payments may be made to compensate for the time spent in extra recruiting efforts.

MSD does not pay for participant referrals. However, MSD may compensate referring physicians for time spent on chart review and medical evaluation to identify potentially eligible participants.

##### **B. Clinical Research Funding**

Informed consent forms will disclose that the trial is sponsored by MSD, and that the investigator or sponsoring institution is being paid or provided a grant for performing the trial. However, the local ethics committee may wish to alter the wording of the disclosure statement to be consistent with financial practices at that institution. As noted above, all publications resulting from MSD trials will indicate MSD as a source of funding.

##### **C. Funding for Travel and Other Requests**

Funding of travel by investigators and support staff (e.g., to scientific meetings, investigator meetings, etc.) will be consistent with local guidelines and practices.

#### **V. Investigator Commitment**

Investigators will be expected to review MSD's Code of Conduct as an appendix to the trial protocol, and in signing the protocol, agree to support these ethical and scientific standards.

##### **10.1.2 Financial Disclosure**

Financial Disclosure requirements are outlined in the US Food and Drug Administration Regulations, Financial Disclosure by Clinical Investigators (21 CFR Part 54). It is the Sponsor's responsibility to determine, based on these regulations, whether a request for Financial Disclosure information is required. It is the investigator's/subinvestigator's responsibility to comply with any such request.

The investigator/subinvestigator(s) agree, if requested by the Sponsor in accordance with 21 CFR Part 54, to provide his/her financial interests in and/or arrangements with the Sponsor to allow for the submission of complete and accurate certification and disclosure statements. The investigator/subinvestigator(s) further agree to provide this information on a Certification/Disclosure Form, commonly known as a financial disclosure form, provided by the Sponsor. The investigator/subinvestigator(s) also consent to the transmission of this information to the Sponsor in the United States for these purposes. This may involve the transmission of information to countries that do not have laws protecting personal data.

##### **10.1.3 Data Protection**

The Sponsor will conduct this study in compliance with all applicable data protection regulations.

Participants will be assigned a unique identifier by the Sponsor. Any participant records or datasets that are transferred to the Sponsor will contain the identifier only; participant names or any information that would make the participant identifiable will not be transferred.

The participant must be informed that his/her personal study-related data will be used by the Sponsor in accordance with local data protection law. The level of disclosure must also be explained to the participant.

The participant must be informed that his/her medical records may be examined by Clinical Quality Assurance auditors or other authorized personnel appointed by the Sponsor, by appropriate IRB/IEC members, and by inspectors from regulatory authorities.

#### **10.1.3.1      Confidentiality of Data**

By signing this protocol, the investigator affirms to the Sponsor that information furnished to the investigator by the Sponsor will be maintained in confidence, and such information will be divulged to the IRB, IEC, or similar or expert committee; affiliated institution and employees, only under an appropriate understanding of confidentiality with such board or committee, affiliated institution and employees. Data generated by this study will be considered confidential by the investigator, except to the extent that it is included in a publication as provided in the Publications section of this protocol.

